9.6. Informed Consent

Written informed consent for the study will be obtained from all subjects before protocol-specific procedures are carried out. The ICF will be approved (along with the protocol) by the IRB and will be acceptable to the Sponsor.

The Investigator (or designee) will explain the nature of the study and the action of the test product. The subjects will be informed that participation is voluntary and that they can withdraw from the study at any time. In accordance with 21 CFR 50, the informed consent process shall be documented by the use of a written ICF approved by the IRB and signed by the subject prior to protocol-specific procedures being performed.

The subject will sign 2 copies of the ICF. One copy will be given to the subject, and the other will be maintained with the subject's records.

9.7. Records

The results from data collected at Screening and during the study will be recorded in the subject's eCRF. To maintain confidentiality, the subjects will be identified only by numbers.

The completed eCRFs will be transferred to the Sponsor (or designee). Copies of each eCRF will be retained by the Investigator (or designee). All source documents, records, and reports will be retained by the CRU in accordance with 21 CFR 312.62(c).

Protocol	CONFIDENTIAL
Covance Study: 8419666	Protocol Reference: LOXO-BTK-20006

All primary data, or copies thereof (eg, laboratory records, eCRFs, data sheets, correspondence, photographs, and computer records), which are a result of the original observations and activities of the study and are necessary for the reconstruction and evaluation of any study report, will be retained in the CRU archives.

9.8. Reference to Declaration of Helsinki/Basic Principles

The study procedures outlined in this protocol will be conducted in accordance with the US CFR governing Protection of Human Subjects (21 CFR 50), Financial Disclosure by Clinical Investigators (21 CFR 54), IRBs (21 CFR 56), Investigational New Drug Application (21 CFR 312), Applications for FDA Approval to Market a New Drug (21 CFR 314), and Radioactive Drugs for Certain Research Uses (21 CFR 361.1), as appropriate. As such, these sections of US Title 21 CFR, along with the applicable International Council for Harmonisation (ICH) Guidelines, are commonly known as Good Clinical Practices (GCP), which are consistent with the Declaration of Helsinki.

9.9. Financing and Insurance

Financing and insurance will be addressed in a separate agreement.

11. APPENDICES

Appendix 1: Adverse Event Reporting

Adverse Events

Definition of Adverse Events

An adverse event (AE; or adverse experience) is defined as any untoward medical occurrence experienced by a patient or healthy adult subject, whether or not considered drug-related by the Investigator (or designee). A treatment-emergent adverse event (TEAE) is an AE that is reported after a dose of study drug.

The following are all AEs:

- unfavorable changes in general condition;
- subjective or objective signs/symptoms;
- concomitant diseases or accidents;
- clinically relevant adverse changes in laboratory parameters observed in a subject during a clinical study.

Adverse events comprise all disturbances of general health status, subjective and objective disease symptoms (including laboratory abnormalities that are deemed clinically significant by the Investigator or designee), and accidents observed in the context of a clinical trial, irrespective of a possible causal relationship with the administration of the trial substance.

Categorization of Adverse Events

The severity of AEs will be categorized based on the National Cancer Institute Common Terminology Criteria for Adverse Events (CTCAE) Version 5.0 as follows:

- **Grade 1 Mild:** Asymptomatic or mild symptoms; clinical or diagnostic observations only; intervention not indicated
- **Grade 2 Moderate:** Minimal, local or noninvasive intervention indicated; limiting age-appropriate instrumental Activities of Daily Living (ADL)*
- Grade 3 Severe or medically significant but not immediately life-threatening: Hospitalization or prolongation of hospitalization indicated; disabling; limiting self-care ADL**
- Grade 4 Life-threatening consequences: An event that puts the patient at immediate risk of death
- **Grade 5** Death related to AE.

Note: Not all grades are appropriate for all AEs. Therefore, some AEs are listed within the CTCAE with fewer than 5 options for grade selection. Grade 5 (death) is not appropriate for some AEs and therefore is not an option. * Instrumental ADL refer to preparing meals, shopping for groceries or clothes, using the telephone, managing money, etc. **Self-care ADL refer to bathing, dressing and undressing, feeding self, using the toilet, taking medications, and not bedridden. The Investigator (or designee) will make a determination of the relationship of the AE to the study drug using a 2-category system according to the following guidelines:

- **NOT RELATED** = The time course between the administration of investigational product and the occurrence or worsening of the AE rules out a causal relationship and another cause (eg, concomitant drugs, therapies, complications, comorbidities) is suspected.
- **RELATED** = The time course between administration of investigational product and the occurrence or worsening of the AE is consistent with a causal relationship and no other cause (eg, concomitant drugs, therapies, complications, comorbidities) can be identified.

An AE is associated with the use of the drug if there is a reasonable possibility that the experience may have been caused by the drug.

Pregnancy

As information is available, a pregnancy (including pregnancy in female partners of male subjects) diagnosed through End of Study (EOS) or Early Termination (ET; if the subject discontinues from the study and does not complete a follow-up phone call) and for up to 90 days after study drug administration should be reported by the Investigator (or designee) via email to Covance or the Sponsor's Clinical Safety Representative within 24 hours of being notified. Covance or the Sponsor's Clinical Safety Representative will then forward the Pregnancy Form to the Investigator for completion.

email: [contact]

A subject becoming pregnant while on study drug will immediately be withdrawn from the study and ET study procedures will be performed. The subject or partner should be followed by the Investigator until completion of the pregnancy. If the pregnancy ends for any reason before the anticipated date, the Investigator should notify Covance or the Sponsor's Clinical Safety Representative. At the completion of the pregnancy, the Investigator will document the outcome of the pregnancy. If the outcome of the pregnancy meets the criteria for immediate classification as a serious adverse event (SAE; ie, postpartum complication, spontaneous abortion, stillbirth, neonatal death, or congenital anomaly), the Investigator should follow the procedures for reporting an SAE.

Male subjects will be instructed to notify the Investigator immediately if they discover their sexual partner is pregnant. In this instance, the partner must provide written consent before pregnancy information can be collected. When a Clinical Research Unit (CRU) becomes aware that the female partner of a male subject is pregnant, they are to contact the Investigator immediately (within 24 hours of the CRU staff becoming aware of the event) in addition to notifying Covance or the Sponsor's Clinical Safety Representative via email.

All pregnancies should be recorded on the AE electronic Case Report Form (eCRF; as appropriate), in addition to completion of the required pregnancy forms. If the Investigator suspects that a pregnancy was the result of an interaction between the study treatment and the contraceptive method, in addition to the pregnancy the drug interaction should also be captured as a separate AE.

Definition of Serious Adverse Events

An SAE (by Food and Drug Administration [FDA] definition) is any adverse drug experience occurring at any dose that results in any of the following outcomes:

- Death;
- A life-threatening adverse drug experience (ie, one that places the subject, in the view of the Investigator [or designee], at immediate risk of death);
- Inpatient hospitalization or prolongation of existing hospitalization;
- A persistent or significant disability/incapacity;
- A congenital anomaly/birth defect;
- An important medical event that may require medical or surgical intervention to prevent one of the above outcomes.

Important medical events that may not result in death, be life-threatening, or require hospitalization may be considered SAEs when, based on appropriate medical judgment, they may jeopardize the patient or subject and may require medical or surgical intervention to prevent one of the outcomes listed in this definition.

Unexpected Adverse Drug Reaction

An AE or suspected adverse drug reaction is considered 'unexpected' if the event is not listed in the Reference Safety Information section of the Investigator's Brochure (IB) or if it is not listed at the specificity or severity that has been observed for an unapproved investigational medicinal product (IMP).

Reporting

Food and Drug Administration-reportable AEs are AEs that are associated with the use of the drug and represent events that are assessed as serious, related, and unexpected. Food and Drug Administration-reportable AEs will be reported by the CRU to the Sponsor and the responsible Institutional Review Board (IRB). Final determination of whether an event represents a suspected unexpected serious adverse reaction (SUSAR) will be the responsibility of the Sponsor.

Within 24 hours of when an AE that is potentially FDA-reportable is first recognized or reported, and within 24 hours of any SAE (regardless of whether the event is assessed as related or unrelated to study drug) being first recognized or reported, Covance or the Sponsor's Clinical Safety Representative will be notified by the Investigator or designee in writing using the following email address:

email: [contact]

To report the SAE, the completed report form should be sent by email to Covance or the Sponsor's Clinical Safety Representative within 24 hours of awareness. Incoming reports are reviewed during normal business hours. Additional reporting instructions and the SAE Report Form are provided in the Study Manual.

The IRB will be notified of any FDA-reportable AE within the timeframe required by the IRB. The IRB Serious and Unexpected Adverse Experience Submission Form will be completed and submitted with the copy of the written confirmation or summary of the AE.

Clinical Chemistry Panel (Fasted):	Complete Blood Count (CBC):	Other Tests:
Alanine aminotransferase (ALT)	Hematocrit	Hemoglobin A1c (HbA1c) ^b
Albumin	Hemoglobin	Thyroid-stimulating hormone
Alkaline phosphatase (ALP)	Mean corpuscular hemoglobin	(TSH) ^b
Amylase	Mean corpuscular hemoglobin	Coagulation Parameters:
Aspartate aminotransferase	concentration	Activated partial thrombin time
(AST)	Mean corpuscular volume	Partial thromboplastin time
Bilirubin (direct and total)	Platelet count	Prothrombin time
Blood urea nitrogen	Red blood cell (RBC) count	International normalized ratio
Calcium	RBC distribution width	
Chloride	White blood cell (WBC) count	Serology:"
Cholesterol	WBC differential (percent and	Human immunodeficiency virus
Creatine kinase (CK)	absolute):	(HIV) antibody
Creatinine	Basophils	Hepatitis B surface antigen
Glucose	Eosinophils	(HBsAg)
Iron	Lymphocytes	Hepatitis C virus (HCV)
Lipase	Monocytes	antibody
Magnesium	Neutrophils	For Female Subjects only:
Phosphorus		
Potassium		pregnancy test (serum
Sodium	Urinalysis:	qualitative, seruin qualitative
Total protein	Bilirubin	may be used for communation in
Triglycerides	Color and appearance	E alliala atimulatina hannana
Uric acid	Glucose	romcle-sumulating normone
	Ketones	(post-menopausai female
	Leukocyte esterase	Subjects only)
	Nitrite	Estimated creatinine clearance
Urine Drug Screen: ^a	Occult blood	
Including but not limited to the	pH and specific gravity	
following:	Protein	
Alcohol (ethanol) (breath test)	Urobilinogen	
Amphetamines	Microscopic examination	
Barbiturates	including bacteria, casts,	
Benzodiazepines	crystals, epithelial cells, RBCs,	
Cannabinoids	and WBCs (if protein, leukocyte	
Cocaine (metabolite)	esterase, nitrite, or blood is	
Methadone	positive)	
Opiates		
Phencyclidine		
Cotinine		

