1.4.1. Safety

As of 27 September 2019, 27 (96.4%) of the 28 patients were continuing treatment; 1 patient in the 25 mg QD cohort discontinued treatment due to progressive disease and withdrew consent.

Overall, 22 (78.6%) patients experienced at least 1 treatment-emergent adverse event (TEAE), regardless of relationship to study drug. Treatment-emergent adverse events were coded according to the Medical Dictionary for Regulatory Activities (MedDRA) system organ class (SOC) and preferred term (PT). Across the 25 mg to 200-mg QD dose range, the most frequently reported TEAEs (> 10% of patients), regardless of relationship to study drug, were fatigue (25.0%), diarrhea (17.9%), anemia (14.3%), arthralgia (10.7%), back pain (10.7%), increased blood bilirubin (10.7%), contusion (10.7%), and maculo-papular rash (10.7%).

As of the date cut off of 27 September 2019, most TEAEs were mild or moderate (Grade 1 or 2) in severity. Grade 3 TEAEs have been reported in 2 patients to date (1 with neutropenia

and 1 with leukocytosis, the latter also reported as a serious adverse event [SAE]). Both of these were judged by the Investigator to be related to the study drug.

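### The two causality categories in Protocol Appendix 1 are not exhaustive: an AE with compatible timing and an identified other cause is neither RELATED nor NOT RELATED

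*Protocol*

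**What the plan says.** Under Protocol Appendix 1 (Categorization of Adverse Events), the rater "will make a determination of the relationship of the AE to the study drug using a 2-category system according to the following guidelines". Two definitions follow.

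- NOT RELATED: the time course "rules out a causal relationship and another cause (eg, concomitant drugs, therapies, complications, comorbidities) is suspected".
- RELATED: the time course "is consistent with a causal relationship and no other cause (eg, concomitant drugs, therapies, complications, comorbidities) can be identified".

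A separate sentence then treats an event as drug-associated "if there is a reasonable possibility that the experience may have been caused by the drug". Under Reporting in the same appendix, FDA-reportable AEs are those "associated with the use of the drug and represent events that are assessed as serious, related, and unexpected".

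The rating is used in these places:

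- SAP 8.6.1 summarises treatment-related TEAEs by treatment, severity, system organ class and preferred term. It takes the investigator's rating and counts a relationship to LOXO-305, itraconazole or rifampin. Protocol 8.4 also plans AE incidence by relationship.
- Protocol 3.1.3 and 7.2.1 restrict AE reporting between EOT or ET and EOS to events rated related. SAEs are reported throughout.
- Protocol 4.6 and 7.2.1 allow, but do not require, continued follow-up of related AEs still ongoing at ET or EOS.

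**The concern.** A two-category scale works only if every event falls into one category. Here each category needs two conditions at once, and the two definitions are not complements of each other. The gap falls on a kind of event that a safety review cares about: the drug could have caused it on timing, but something else could have too. The investigator must still choose, and the text gives no basis for the choice. Two raters could classify the same event differently, and the direction of the error cannot be predicted.

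Safety and tolerability are the secondary objectives, and the treatment-related summaries rest directly on this rating. After EOT or ET the rating also decides whether a non-serious event is reported at all.

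**Working it through.** The plan states no figure to reproduce. The check is to set the two definitions against the possible combinations of timing and other cause.

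**Inputs.** The two definitions, the lead-in and the association sentence (Protocol Appendix 1); 12 subjects per part (Protocol 8.1); follow-up call 7 ± 2 days after EOT or ET (Protocol 7.2.1); the treatment-related definition and the missing-data rule (SAP 8.6.1).

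**Step 1: combinations.**

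- Timing consistent, no other cause identified: RELATED. This holds even if another cause is merely suspected, because the definition turns on whether one can be identified.
- Timing rules out causality, another cause suspected or identified: NOT RELATED.
- Timing consistent, another cause identified: RELATED fails on its second condition and NOT RELATED fails on its first. No category applies.
- Timing rules out causality, no other cause suspected: no category applies here either. This is harmless in practice, since timing has already excluded the drug.

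The third combination is the one that matters.

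**Step 2: comparison with the association sentence.** The reasonable-possibility test does not ask whether other causes exist. An event in the third combination can pass it and still fail RELATED. RELATED is therefore the stricter standard, and the FDA-reportable definition requires both.

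**Step 3: does another rule close the gap?** SAP 8.6.1 treats a missing relationship as related. A rating forced into one of two boxes is not missing, so that rule does not apply.

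**Step 4: the term used.** The lead-in rates the relationship to the study drug, but both definitions refer to something else, as in "The time course between administration of investigational product and the occurrence or worsening of the AE". The documents do not define investigational product. The Introduction uses the singular investigational medicinal product for the product described in the Investigator's Brochure. The synopsis heading uses the plural over all three drugs. If the term were read as LOXO-305 alone, itraconazole or rifampin could be taken as a concomitant drug, which the definitions list among other causes. The lead-in and SAP 8.6.1 point to the broader reading, so this is a small inconsistency.

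**Step 5: scale.**

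- One subject whose only event changes category moves a treatment-related incidence by 1/12 = 8.3 percentage points within a part. This is the step size of any yes/no item with 12 subjects; it does not estimate how often the problem arises.
- The window in which relatedness decides reporting of a non-serious AE runs to the call at 7 − 2 = 5 to 7 + 2 = 9 days after EOT or ET.

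**The case against.** The strongest reply is that the definitions are only guidelines for a judgement, and that the reasonable-possibility sentence directly after them can be read as the test that settles whatever they leave open. That reading is possible, but the appendix does not state it. The sentence defines association, a word that the Reporting text lists separately from related. An investigator applying the definitions as written still has no answer.

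A second reply is that little depends on the rating, and much of this stands. Safety analysis is descriptive, all AEs are collected through EOT or ET whatever their relationship, all TEAEs are summarised, and the extra follow-up is optional. Healthy subjects and restricted medication (Protocol 4.4 and 6.1) also limit competing causes.

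A reader might infer that serious events could escape regulatory reporting because they fail RELATED. The documents do not support that. FDA-reportable events are by definition serious, and Appendix 1 requires notice of every SAE within 24 hours regardless of relatedness. The sponsor makes the final SUSAR determination, and Protocol 9.5 has the IRB informed of serious and unexpected AEs. What remains is an inconsistent definition of the label.

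A reader might also infer that the wording leaves unclear which drugs count in the analysis. SAP 8.6.1 settles that by naming all three.

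**Conclusion.** The definitions are wrong as written, and the severity is minor. An AE with compatible timing and an identified other cause has no category, and RELATED is stricter than the reasonable-possibility test beside it. The consequence is rater-dependent classification, confined mainly to the treatment-related TEAE summaries and to the reporting of non-serious AEs between EOT or ET and EOS. The effect on FDA-reportable status is limited, for the reasons given above.

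The conclusion rests on reading each definition as requiring both of its conditions, which is what the wording says. How often the gap would be met cannot be derived: the documents give no rate, and the number of empty combinations is not a frequency. The Study Manual may hold further reporting instructions, but it is not among the documents.

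**What to change.** In Protocol Appendix 1, base both categories on the protocol's own test:

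- RELATED: there is a reasonable possibility that a study drug caused the event, even if another cause exists.
- NOT RELATED: there is no reasonable possibility that a study drug caused the event.

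In both definitions, replace investigational product with study drug (LOXO-305, itraconazole or rifampin), which matches SAP 8.6.1. The word related should keep this one meaning throughout the appendix, including under Reporting.

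The cost is a wording amendment, agreed between sponsor and investigator (Protocol 9.1) and submitted to the IRB (Protocol 9.5). No assessment or table is added, and SAP 8.6.1 can stand. The downside is that somewhat more events will be rated related.

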Appendix 2: Clinical Laboratory Evaluations

a. Performed at Screening and Check-in (Day -1) only.

b. Performed at Screening only.

c. Performed at Screening, Check-in (Day -1), and End of Treatment (EOT)/Early Termination (ET) only.

Appendix 3: Total Blood Volume

Part 1: Itraconazole (CYP3A4 and P-gp Inhibitor)

The following blood volumes will be withdrawn for each subject participating in Part 1:

	Approximate Blood Volume per Sample	Maximum Number of Blood	Approximate Total Volume
Assessment	(mL)	Samples	(mL)
Serology	4.0	1	4.0
Hemoglobin A1c (HbA1c)	4.0	1	4.0
Primary pharmacokinetic (PK) sampling	4.0	40	160.0
Clinical laboratory tests:			
Complete blood count (CBC)	4.0	7	28.0
Clinical chemistry	4.0	7	28.0
Coagulation parameters	3.0	7	21.0
Serum pregnancy test (female subjects only)	4.0	3	12.0
Serum follicle-stimulating hormone (FSH; post-menopausal female subjects only)	4.0	1	4.0
Thyroid-stimulating hormone (TSH)	4.0	1	4.0
		Total:	265.0 mL

If extra blood samples are required, the maximum blood volume to be withdrawn per subject will not exceed 350 mL in Part 1.

Part 2 – Rifampin (CYP3A4 Inducer)

The following blood volumes will be withdrawn for each subject participating in Part 2:

Assessment	Approximate Blood Volume per Sample (mL)	Maximum Number of Blood Samples	Approximate Total Volume (mL)
Serology	4.0	1	4.0
Hemoglobin A1c (HbA1c)	4.0	1	4.0
Primary pharmacokinetic (PK) sampling	4.0	53	212.0
Clinical laboratory tests:			
Complete blood count (CBC)	4.0	8	32.0
Clinical chemistry	4.0	8	32.0
Coagulation parameters	3.0	8	24.0
Serum pregnancy test (female subjects only)	4.0	3	12.0
Serum follicle-stimulating hormone (FSH; post-menopausal female subjects only)	4.0	1	4.0
Thyroid-stimulating hormone (TSH)	4.0	1	4.0
		Total:	328.0 mL

If extra blood samples are required, the maximum blood volume to be withdrawn per subject will not exceed 410 mL in Part 2.

Appendix 4: Schedule of Assessments

Protocol Covance Study: 8419666

Part 1 – Itraconazole (CYP3A4 and P-gp Inhibitor)

					Pe	eriod	11							P		Clinic	Follow-up Phone Call (EOS)					
Study Procedures ^a	Screening (Days -29 to -2)	Check-in (Day -1)	1	2	3	4	5	6	7	8	9	10	11	12	13	14	15	16	17	18	Discharge/ EOT (Day 19) or ET ^r	7 (±2) days post EOT or ET ^s
Confined to the CRU		Х	Х	Х	Х	Х	Х	Х	Х	Х	Х	Х	Х	Х	Х	Х	Х	Х	Х	Х	Х	
Inclusion/Exclusion Criteria	Х	Х																				
Informed Consent	Х																					
Demographics	Х																					
Medical History	Х	Xb																				
Height/Weight/BMI	Х	Xc																				
Physical Examination ^d	Х	Х																			X	
12-lead ECG ^e	Х	Х	Χ			Χ				Χ				Χ			Χ				X	
Vital Signs ^f	Х	Х	Χ			Χ				Χ				Χ			Χ				X	
HDYF? Inquiry ^g	Х	Х	Х	Χ	Χ	Х	Χ	Χ	Χ	Χ	Χ	Х	Χ	Χ	Χ	Χ	Χ	Χ	Χ	Χ	Х	X
AEs/SAEs ^h	Х	Х	Χ	Х	Χ	Χ	Χ	Χ	Χ	Χ	Χ	Х	Χ	Х	Х	Х	Χ	Х	Χ	Χ	X	X
LOXO-305 Dosing ⁱ			Χ											Χ								
Itraconazole Dosing ^j										Χ	Χ	Х	Χ	Х	Х	Х	Χ	Х	Χ	Χ		
CCI			C	C																		
Clinical Laboratory Evaluations ¹	х	Х				x			x				X				X				X	
Hepatitis and HIV Screen	X																					
HbA1c Test ^m	Х																					
Drug Screen ⁿ	Х	X																				

Protocol Version 1, 14 January 2020

Protocol Covance Study: 8419666

					P	erioc	11							P	eriod	12					Clinic	Follow-up Phone Call (EOS)
Study Procedures ^a	Screening (Days -29 to -2)	Check-in (Day -1)	1	2	3	4	5	6	7	8	9	10	11	12	13	14	15	16	17	18	Discharge/ EOT (Day 19) or ET ^r	7 (±2) days post EOT or ET ^s
Prior and Concomitant Medications ^o	X	Х	X	X	X	X	X	X	X	X	X	X	X	X	X	X	X	X	X	X	Х	Х
Serum Pregnancy Test ^p	X	Х																			Х	
FSH Test ^q TSH Test	X X																					

Abbreviations: AE = adverse event; BID = twice daily; BMI = body mass index; BP = blood pressure; CBC = complete blood count; CK = creatine kinase; CRU = Clinical Research Unit; ECG = electrocardiogram; EOS = End of Study; EOT = End of Treatment; ET = Early Termination; FSH = follicle-stimulating hormone; HDYF? = How Do You Feel?; HIV = human immunodeficiency virus; ICF = Informed Consent Form; PK = pharmacokinetic; SAE = serious adverse event; TSH = thyroid-stimulating hormone; UA = urinalysis.

a. For details on study procedures, see Section 7.

b. Interim medical history only.

c. Weight and BMI (based on Screening height) only.

d. A complete physical examination will be performed at Screening. An abbreviated physical examination will be performed at Check-in (Day -1) and at EOT (Day 19).

- e. 12-lead ECGs will be collected after the subject has rested in the supine position for at least 10 minutes, and will be obtained prior to and as close as possible to the scheduled blood draws at Screening and Day -1, Day 1 (predose and 2 hours after LOXO-305 dosing), Day 4 (ie, 72 hours after LOXO-305 dosing on Day 1), Day 8 (ie, 168 hours after LOXO-305 dosing on Day 1), Day 12 (before LOXO-305 and itraconazole dosing), Day 15 (ie, 72 hours after LOXO-305 and itraconazole dosing on Day 12), and at EOT/Day 19 (168 hours after LOXO-305 and itraconazole dosing on Day 12).
- f. Vital signs measurements (oral temperature, respiratory rate, and supine BP and pulse rate) will be obtained at Screening and Day -1, Day 1 (predose and 2 hours after LOXO-305 dosing), Day 4 (ie, 72 hours after LOXO-305 dosing on Day 1), Day 8 (ie, 168 hours after LOXO-305 dosing on Day 1), Day 12 (before LOXO-305 and itraconazole dosing), Day 15 (ie, 72 hours after LOXO-305 and itraconazole dosing on Day 12), and at EOT/Day 19 (168 hours after LOXO-305 and itraconazole dosing on Day 12). Vital signs measurements should be carried out prior to and as close as possible to having blood drawn. Blood pressure and pulse rate will be measured using the same arm for each reading after the subject has been supine for at least 5 minutes.
- g. An HDYF? inquiry will be performed at Screening (after the ICF is signed), at Check-in (Day -1), at each postdose vital signs assessment, and at an appropriate time for all other days.
- h. Adverse events and SAEs will be collected beginning at informed consent. Adverse events will be recorded throughout the study (ie, from signing of the ICF until EOS, or until ET if the subject discontinues from the study and does not complete a follow-up phone call), either as subject medical history (if the event is reported as beginning prior to signing of the ICF or if the event occurs prior to study drug administration on Day 1 and is assessed as not related to study procedures by the Investigator [or designee]) or as AEs (if the event occurs after signing of the ICF but prior to study drug administration on Day 1 and is assessed by the Investigator [or designee]) as related to study procedures, or if the event occurs after study drug administration on Day 1 and is assessed by the Investigator [or designee]) as related to study procedures, or if the event occurs after study drug administration on Day 1 and is assessed by the Investigator [or designee]) as related to study procedures, or if the event occurs after study drug administration on Day 1 and is assessed by the Investigator [or designee]) as related to study procedures.

Protocol	CONFIDENTIAL
Covance Study: 8419666	Protocol Reference: LOXO-BTK-20006

Day 1 through EOT or ET regardless of relationship to study drug). From EOT or ET through EOS, only AEs assessed as related to study drug are to be recorded. All SAEs that develop from the time of ICF signing until EOS (or ET if the subject discontinues from the study and does not complete a follow-up phone call) are to be reported.

- i. On Day 1, LOXO-305 will be administered in the morning following a fast of at least 10 hours prior to and 4 hours after the LOXO-305 dose. On Day 12, LOXO-305 will be co-administered with itraconazole in the morning following a fast of at least 10 hours prior to and 4 hours after dosing with LOXO-305 and itraconazole.
- j. On Day 8, BID doses of itraconazole will be administered. On Days 9 to 18 (inclusive), QD doses of itraconazole will be administered. On Day 12, itraconazole will be co-administered with LOXO-305 in the morning following a fast of at least 10 hours prior to and 4 hours after dosing with LOXO-305 and itraconazole. On Day 8, when itraconazole will is administered BID, the morning dose will be administered alone at the actual time of the Day 1 LOXO-305 dose (± 1 hour), approximately 30 minutes after starting a standard breakfast, and the evening dose will be administered approximately 10 (±1) hours after the morning dose, approximately 30 minutes after starting a standard evening meal. On Days 9 to 11 and Days 13 to 18, the QD dose of itraconazole will be administered alone at the actual time of the Day 1 LOXO-305 dose (± 1 hour), approximately 30 minutes after the start of a standard breakfast. All meals should be entirely consumed within 30 minutes.

- 1. Clinical chemistry panel including CK (fasted at least 8 hours), coagulation parameters, CBC, and UA will be performed at Screening, Check-in (Day -1), Days 4 and 7, and Days 11 and 15 (before itraconazole dosing), and at EOT (Day 19) or ET.
- m. Hemoglobin A1c test performed at Screening only.
- n. Alcohol breath test and drugs of abuse urine test, including cotinine. Results from the alcohol and drug tests will be used to determine subject eligibility per the inclusion/exclusion criteria.
- Prior and concomitant medication administration will be recorded beginning at informed consent. In addition, all Investigator-approved medications taken by a subject within 30 days prior to study drug administration for prescription medications, and 14 days prior to study drug administration for non-prescription medications, will be recorded on the subject's electronic Case Report Form.
- p. Female subjects only.
- q. Post-menopausal female subjects only.
- r. EOT is defined as when the subject is released from the CRU following completion of all assessments through Day 19. ET is defined as when the subject is released from the CRU if the subject terminates the study early. Vital signs, ECG, and safety laboratory results for clinical chemistry, hematology, coagulation, and UA are to be available for review by the Investigator or designee prior to subject release from the CRU at the EOT or ET visit.
- s. To be performed 7 days (± 2 days) following EOT or ET. EOS is defined as when the CRU contacts the subject by a follow-up phone call 7 days (± 2 days) after the EOT visit or ET visit to determine if any SAE or study drug-related AE has occurred since the EOT or ET visit. All subjects who received LOXO-305 (including subjects who are terminated early) will be contacted.

Protocol Covance Study: 8419666

Part 2 – Rifampin (CYP3A4 Inducer)

					Period 1]	Peri	iod 2	2							Clinic	Follow-up Phone Call (EOS)
Study Procedures ^a	Screening (Days -29 to -2)	Check-in (Day -1)	1	2	3	4	5	6	7	8	9	10	11	12	13	14	15	16	17	18	19	20	21	22	23	Discharge/ EOT (Day 24) or ET ^s	7 (±2) days post EOT or ET ^t
Confined to the CRU		X	x	X	x	x	x	x	X	X	X	x	X	x	x	x	x	x	x	X	x	X	X	X	X	X	
Inclusion/Exclusion Criteria	х	Х																									
Informed Consent	Х																										
Demographics	Х																										
Medical History	Х	Xb																									
Height/Weight/BMI	X	Xc																									
Physical Examination ^d	х	X																								X	
12-lead ECG ^e	Х	Х	Х			Х				Х			Х						Х			Х				X	
Vital Signs ^f	Х	Х	Х			Х				Х			Х						Х			Х				X	
HDYF? Inquiry ^g	Х	Х	Х	Χ	Х	Х	Х	Х	Х	Х	Х	Х	Х	Х	Х	Х	Х	Х	Χ	Χ	Χ	Х	Х	Χ	Х	X	Х
AEs/SAEs ^h	Х	X	Х	Х	Х	Х	Х	Х	Х	Х	Х	Х	Х	Х	Х	Х	Х	Х	Х	Х	Х	Х	Х	Х	Х	X	Х
LOXO-305 Dosing ⁱ			Х							Х									Х								
Rifampin Dosing ^j										Х	Х	Х	Х	Χ	Х	Χ	Х	Χ	Χ	Χ	Χ	Х	Х	Х	Χ		
CCI			C	C																							

Protocol Covance Study: 8419666

					Pe	erio	d 1			Period 2																Clinic	Follow-up Phone Call (EOS)
Study Procedures ^a	Screening (Days -29 to -2)	Check-in (Day -1)	1	2	3	4	5	6	7	8	9	10	11	12	13	14	15	16	17	18	19	20	21	22	23	Discharge/ EOT (Day 24) or ET ^s	7 (±2) days post EOT or ET ^t
Urine Samples for 6β-hydroxycortisol and Free Cortisol Concentrations ¹										X			X				x		x								
Clinical Laboratory Evaluations ^m	X	X				X			X				X					X				X				X	
Hepatitis and HIV Screen	Х																										
HbA1c Test ⁿ	Х																										
Drug Screen ^o	Х	Х																									
Prior and Concomitant Medications ^p	X	X	X	x	X	x	x	x	x	x	x	x	x	X	x	X	x	x	x	x	x	x	x	x	X	X	Х
Serum Pregnancy Test ^q	X	X																								X	
FSH Test ^r	Х																										
TSH Test	X																										

 I SH Test
 X
 Image: Abbreviations: AE = adverse event; BMI = body mass index; BP = blood pressure; CK = creatine kinase; CRU = Clinical Research Unit; ECG = electrocardiogram; EOS = End of Study; EOT = End of Treatment; ET = Early Termination; FSH = follicle-stimulating hormone; HbA1c = hemoglobin A1c; HDYF? = How Do You Feel?; HIV = human immunodeficiency virus;

ICF = Informed Consent Form; PK = pharmacokinetic; QD = once daily; SAE = serious adverse event; TSH = thyroid-stimulating hormone; UA = urinalysis.

a. For details on study procedures, see Section 7.

b. Interim medical history only.

c. Weight and BMI (based on Screening height) only.

d. A complete physical examination will be performed at Screening. An abbreviated physical examination will be performed at Check-in (Day -1) and at EOT (Day 24).

e. 12-lead ECGs will be collected after the subject has rested in the supine position for at least 10 minutes, and will be obtained prior to and as close as possible to the scheduled blood draws at Screening and Day -1, Day 1 (predose and 2 hours postdose after LOXO-305 dosing), Day 4 (72 hours after LOXO-305 dosing), Day 8 (168 hours after LOXO-305 dosing and predose of

Protocol	CONFIDENTIAL
Covance Study: 8419666	Protocol Reference: LOXO-BTK-20006

LOXO-305 and rifampin dosing), Day 11 (72 hours after LOXO-305 and rifampin dosing). Day 17 (predose of LOXO-305 and rifampin dosing), Day 20 (72 hours after LOXO-305 and rifampin dosing), and at EOT (168 hours postdose [ie, Day 24] of LOXO-305 and rifampin dosing).

- f. Vital signs measurements (oral temperature, respiratory rate, and supine BP and pulse rate) will be obtained at Screening and Day -1, Day 1 (predose and 2 hours after LOXO-305 dosing), Day 4 (72 hours after LOXO-305 dosing), Day 8 (168 hours postdose (LOXO-305 dosing and predose of LOXO-305 and rifampin dosing), Day 11 (72 hours after LOXO-305 and rifampin dosing). Day 17 (predose of LOXO-305 and rifampin dosing), Day 20 (72 hours after LOXO-305 and rifampin dosing), and at EOT (168 hours postdose [ie, Day 24] of LOXO-305 and rifampin dosing). Vital signs measurements should be carried out prior to and as close as possible to having blood drawn. Blood pressure and pulse rate will be measured using the same arm for each reading after the subject has been supine for at least 5 minutes.
- g. An HDYF? inquiry will be performed at Screening (after the ICF is signed), at Check-in (Day -1), at each postdose vital signs assessment, and at an appropriate time for all other days.
- h. Adverse events and SAEs will be collected beginning at informed consent. Adverse events will be recorded throughout the study (ie, from signing of the ICF until EOS, or until ET if the subject discontinues from the study and does not complete a follow-up phone call), either as subject medical history (if the event is reported as beginning prior to signing of the ICF or if the event occurs prior to study drug administration on Day 1 and is assessed as not related to study procedures by the Investigator [or designee]) or as AEs (if the event occurs after signing of the ICF but prior to study drug administration on Day 1 and is assessed by the Investigator [or designee]) as related to study procedures, or if the event occurs after study drug administration on Day 1 through EOT or ET regardless of relationship to study drug). From EOT or ET through EOS, only AEs assessed as related to study drug are to be recorded. All SAEs that develop from the time of ICF signing until EOS (or ET if the subject discontinues from the study and does not complete a follow-up phone call) are to be reported.
- i. On Day 1, LOXO-305 will be administered in the morning following a fast of at least 10 hours prior to and 4 hours after the LOXO-305 dose. On Days 8 and 17, LOXO-305 will be co-administered with rifampin in the morning following a fast of at least 10 hours prior to and 4 hours after dosing with LOXO-305 and rifampin.
- j. On Days 8 to 23 (inclusive), QD doses of rifampin will be administered. On Days 8 and 17, rifampin will be co-administered with LOXO-305 in the morning following a fast of at least 10 hours prior to and 4 hours after dosing with LOXO-305 and rifampin. On Days 9 to 16 and Days 18 to 23, the dose of rifampin will be administered alone at the actual time of the Day 1 LOXO-305 dose (± 1 hour), following a fast of at least 8 hours prior to and 2 hours after dosing.

- 1. Urine samples will be collected on the mornings of Days 8, 11, 15, and 17 and may be stored for future potential assessment of 6β-hydroxycortisol and free cortisol concentrations to evaluate the level of CYP3A enzyme induction.
